Appendix D. Study Activities – Optional Samples for Exploratory Research and Validation Studies

Add: new table note "All optional samples for exploratory research and validation studies must be collected at the study site."

All optional samples for exploratory research and validation studies must be collected at the study site.

#### 1.0 Introduction

This Statistical Analysis Plan (SAP) describes the statistical analyses for Study M14-675, A Multicenter, Randomized, Double-Blind, Placebo-Controlled Induction Study to Evaluate the Efficacy and Safety of Upadacitinib (ABT-494) in Subjects with Moderately to Severely Active Ulcerative Colitis.

The analyses of pharmacokinetic endpoints, pharmacodynamic biomarker endpoints and exploratory research and validation endpoints will not be covered in this SAP.

The SAP will not be updated in case of administrative changes or amendments to the protocol unless the changes impact the analysis.

Unless noted otherwise, all analyses will be performed using SAS Version 9.4 (SAS Institute Inc., Cary, NC 27513) or later under the UNIX operating system.

This SAP includes changes to analyses described in the protocol. Details are outlined in Section 13.0.

[figure not shown]
## 2.0 Study Design and Objectives

## 2.1 Objectives, and Hypotheses and Estimands

The objective of the Induction Study is to evaluate efficacy and safety of upadacitinib 45 mg QD compared to placebo in inducing clinical remission (per Adapted Mayo scire) in subjects with moderately to severely active UC who demonstrated inadequate response to, loss of response to, or intolerance to either biologic therapy (Bio-IR) or to conventional therapy (aminosalicylates, corticosteroids or immunosuppressants) but had not failed biologic therapy (non-Bio-IR).

#### **Primary Efficacy Objective**

The primary efficacy objective of the Induction Study is to demonstrate efficacy based on a higher rate of clinical remission per Adapted Mayo score after 8 weeks of treatment with

upadacitinib 45 mg QD when compared to placebo in subjects with moderately to severely active UC who have demonstrated inadequate response, loss of response, or intolerance to oral aminosalicylates, immunosuppressants, corticosteroids, and/or biologic therapies. The primary efficacy objective will be assessed based on Intent-to-Treat (ITT) population, which consists of all randomized subjects who have received at least one dose of double-blinded study drug.

Hypothesis corresponding to the primary efficacy objective and endpoint is:

• The proportion of subjects achieving clinical remission per Adapted Mayo score treated with upadacitinib 45 mg QD is greater than those treated with placebo at Week 8.

The estimand corresponding to the primary efficacy objective is defined as follows:

[figure not shown]
• Difference in the percentage of subjects achieving clinical remission per Adapted Mayo score at Week 8 regardless of premature discontinuation of study drug and without initiation or dose escalation of UC-related corticosteroids (See Section 8.2.2) in the upadacitinib 45 mg QD and placebo groups in the ITT population.

#### **Secondary Efficacy Objectives**

The secondary efficacy objectives of the Induction Study are to demonstrate higher efficacy of treatment with upadacitinib 45 mg QD when compared to placebo with respect to the ranked secondary endpoints specified in Section 3.2. The ranked secondary efficacy objectives will be assessed based on ITT population.

Hypotheses corresponding to the secondary efficacy objectives and endpoints are:

1. For each of the ranked binary secondary endpoints (Section 3.2), greater proportion of subjects with improvement for the endpoint is achieved with upadacitinib 45 mg QD when compared to placebo;

2. For each of the ranked continuous endpoints (Section 3.2), greater mean change from baseline for the endpoint is achieved with upadacitinib 45 mg QD when compared to placebo.

The estimands corresponding to the secondary efficacy objectives are defined for each of the binary ranked secondary endpoints as follows: Difference in the percentage of subjects achieving binary endpoints regardless of premature discontinuation of study drug and without initiation or dose escalation of UC-related corticosteroids (See Section 8.2.2) in the upadacitinib 45 mg QD and placebo groups in the ITT population.

The estimands corresponding to the secondary efficacy objectives are defined for each of the continuous ranked secondary endpoints as follows: difference in the mean change from baseline regardless of premature discontinuation of study drug and if subjects would not initiate or escalate dose of UC-related corticosteroids (See Section 8.2.2) in the upadacitinib 45 mg QD and placebo groups in the ITT population.

#### 2.2 Study Design Overview

This is a Phase 3, multicenter, randomized, double-blind, placebo-controlled study designed to evaluate the efficacy, safety, and pharmacokinetics of upadacitinib as induction therapy in adult subjects with moderately to severely active UC who have been inadequate responders or intolerant to oral aminosalicylates, immunosuppressants, corticosteroids, and/or biologic therapies.

The number of enrolled non-biologic-inadequate responders (non-bio-IR) subjects will be at least 25% and not exceed 50%. Among bio-IR subjects, this study will allow enrollment of up to 30% of subjects who have failed 3 or more biologics. Among non-bio-IR subjects, it will allow enrollment of up to 20% subjects who could also have previous use of biologic therapy but discontinued based on reasons other than inadequate response, loss of response, or intolerance. Subjects who have used a biologic up to 1 year and have discontinued for reasons other than inadequate response, loss of response, or intolerance (e.g., change of insurance/reimbursement, well-controlled disease, etc.) may

[figure not shown]
be enrolled but must meet other criteria for inadequate response, loss of response, or intolerance to aminosalicylates, corticosteroids, or immunosuppressants as defined in the protocol.

#### The study consists of:

[figure not shown]
- 1. Screening period of up to a maximum of 35 days;
- 2. **Part 1:** a randomized, placebo-controlled 8-week double-blind (DB) induction period;
- 3. **Part 2:** an 8-week open-label (OL) extended treatment period for subjects who do not achieve clinical response at Week 8 of Part 1;
- 4. 30-day follow-up period.

The schematics of the study design are shown in Figure 1.

Figure 1. Study Schematic

UPA = Upadacitinib
DB = double blind
QD = once daily
OL = open-label

In Part 1, approximately 462 subjects will be enrolled. Eligible subjects will be randomized in a 2:1 ratio to one of the two treatment groups (DB upadacitinib 45 mg QD or matching placebo) for 8 weeks.

- Group 1: Upadacitinib 45 mg QD (blinded, n = 308)
- Group 2: Placebo QD (blinded, n = 154)

[figure not shown]
Part 2 is an 8-week OL extended treatment period for subjects who did not achieve clinical response at Week 8 in Part 1. The objectives of Part 2 are to offer upadacitinib induction treatment to placebo clinical non-responders from Part 1, and to evaluate delayed clinical response to upadacitinib in subjects who do not initially respond to upadacitinib during Part 1.

Subjects who achieve clinical response at Week 8 (Part 1) or Week 16 (Part 2) will be eligible to enroll into Study M14-234 Substudy 3 (denoted by Maintenance Study thereafter) following written informed consent. Subjects who do not achieve clinical response at Week 16 will be discontinued from the study and will not be eligible to enroll into the Maintenance Study. Subjects who discontinued will complete the 30-Day follow-up visit.

The data collected from subjects in Part 2 will be exploratory in nature and will not be part of the primary efficacy analysis for the study; only descriptive statistics will be provided for Part 2.

#### 2.3 Treatment Assignment and Blinding

In Part 1, approximately 462 subjects will be randomized in a 2:1 ratio to DB upadacitinib 45 mg QD or matching placebo for 8 weeks. The randomization will be stratified by bio-IR status (bio-IR vs. non-bio-IR), corticosteroid use (yes vs. no) and Adapted Mayo score ( $\leq 7 \text{ vs.} > 7$ ) at Baseline. Within bio-IR, the randomization will be further stratified by number of prior biologic treatments ( $\leq 1 \text{ vs.} > 1$ ). Within non-bio-IR, the randomization will be further stratified by previous biologic use (yes vs. no).

All eligible subjects entering Part 2 will receive OL upadacitinib 45 mg QD for an additional 8 weeks (until Week 16).

The primary analysis will be performed after all ongoing subjects have completed the study activities and the database has been locked. Treatment assignments will be unblinded to AbbVie for statistical analyses. The study sites and subjects will remain blinded to the DB induction treatment assignments until all subjects have completed the Maintenance Study.

#### 2.4 Sample Size Determination

For Part 1, approximately 462 subjects are expected to be randomized to upadacitinib 45 mg QD or placebo in a randomization ratio of 2:1. The sample size for this study is based on the expected proportion of subjects who achieve clinical remission per Adapted Mayo score at Week 8. Based on the results from Phase 2b upadacitinib Study M14-234 (Substudy 1), the proportions of subjects achieving clinical remission per Adapted Mayo score in upadacitinib 45 mg QD group and placebo group are 19.6% and 0%, respectively. Considering the small sample size in Phase 2b study and more stringent definition of primary endpoint used for Phase 3 studies, clinical remission rate is assumed to be 5% in the placebo group and 18% in the upadacitinib 45 mg QD treatment group. Based on these assumptions, a sample size of 154 subjects in placebo and 308 subjects in upadacitinib dose will have > 95% power to detect the 13% treatment difference in the primary endpoint between upadacitinib 45 mg QD group and placebo group using two-sided Fisher's exact test at a 0.05 significant level.

## 3.0 Endpoints

The terminologies and efficacy variables are defined as below:

- Mayo Score
  - Full Mayo Score: composite score of UC disease activity based on the stool frequency subscore [SFS] (0-3), rectal bleeding subscore [RBS] (0-3), physician's global assessment [PGA] subscore (0-3) and

[figure not shown]
- endoscopic subscore (0-3). This score ranges from 0-12 points with higher scores representing more severe disease.
- Partial Mayo Score: Full Mayo score minus the endoscopic subscore.
- Adapted Mayo Score: Full Mayo score minus the PGA subscore.
- Partial Adapted Mayo Score: Adapted Mayo score minus the endoscopic subscore.

#### Clinical Remission

- o per Full Mayo Score: Full Mayo score  $\leq 2$  with no subscore  $\geq 1$ .
- o **per Adapted Mayo Score:** Adapted Mayo score  $\leq 2$ , with SFS  $\leq 1$  and not greater than baseline, RBS of 0, and endoscopic subscore  $\leq 1$ .
- o per Partial Mayo Score: Partial Mayo score  $\leq 2$ , with no subscore  $\geq 1$ .

#### • Clinical Response

- per Full Mayo Score: decrease in Full Mayo score of ≥ 3 points and ≥ 30% from Baseline, PLUS a decrease in RBS ≥ 1 or an absolute RBS ≤ 1.
- per Adapted Mayo Score: decrease in Adapted Mayo score ≥ 2 points and ≥ 30% from Baseline, PLUS a decrease in RBS ≥ 1 or an absolute RBS ≤ 1.
- per Partial Mayo Score: decrease in Partial Mayo score ≥ 2 points and ≥ 30% from Baseline, PLUS a decrease in RBS ≥ 1 or an absolute RBS ≤ 1.
- o **per Partial Adapted Mayo Score:** decrease in Partial Adapted Mayo score  $\geq 1$  point and  $\geq 30\%$  from Baseline, PLUS a decrease in RBS  $\geq 1$  or an absolute RBS  $\leq 1$ .
- **Endoscopic Improvement:** Endoscopic subscore of 0 or 1.
- Endoscopic Remission: Endoscopic subscore of 0.
- Histologic Improvement: decrease from Baseline in Geboes score.
- **Histologic Endoscopic Mucosal Improvement:** Endoscopic subscore of 0 or 1 and Geboes score ≤ 3.1.
- **Mucosal Healing:** Endoscopic score of 0 and Geboes score < 2.0.

Note: Evidence of friability during endoscopy in subjects with otherwise "mild" endoscopic activity will confer an endoscopic subscore of 2.

#### 3.1 Primary Endpoint

The primary efficacy endpoint is the achievement of clinical remission per Adapted Mayo score at Week 8 in Part 1.

[figure not shown]
## 3.2 Secondary Endpoints

The ranked secondary efficacy endpoints for Part 1 under overall type I error control are as follows:

[figure not shown]
- 1. The achievement of endoscopic improvement at Week 8;
- 2. The achievement of endoscopic remission at Week 8;
- 3. The achievement of clinical response per Adapted Mayo score at Week 8;
- 4. The achievement of clinical response per Partial Adapted Mayo score at Week 2;
- 5. The achievement of histologic-endoscopic mucosal improvement at Week 8;
- 6. The achievement of no bowel urgency at Week 8;
- 7. The achievement of no abdominal pain at Week 8;
- 8. The achievement of histologic improvement at Week 8;
- 9. Change from Baseline in IBDQ total score at Week 8;
- 10. The achievement of mucosal healing at Week 8;
- 11. Change from Baseline in FACIT-F score at Week 8.

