All subjects will be provided with a Subject Diary (eDiary) at Screening in Study M14-675 where they will record UC-related symptoms, use of anti-diarrheals, and use of medications for endoscopy preparation. For the assessment of the clinical endpoints, the stool frequency and the rectal bleeding subscore will be calculated as an average of the entries recorded into the subject's diary from the most recent consecutive 3-day period prior to each study visit. If diary entries from the 3 consecutive days prior to the visit are not available, the 3 most recent consecutive days in the last 10 days will be utilized. If data is not available for 3 consecutive days, the average of the entries from the most recent 3 non-consecutive days in the last 10 days will be utilized. Clinical endpoints of abdominal pain and bowel urgency from subject diaries will be measured at the same time period as the stool frequency and rectal bleeding subscores. Proportion of subjects who report no abdominal pain and proportion of subjects who report no bowel urgency in the 3 days will be estimated.

At each study visit, a routine physical examination including evaluation of vital signs, evaluation of extra-intestinal manifestations (EIMs), diary review, monitoring for adverse events (AEs), review of concomitant medications, and completion of laboratory assessments will be performed. A full physical examination will be performed at Screening, Baseline, Week 8 and Week 16/Premature Discontinuation (PD) (for subjects who enter the Extended Treatment Period) and must include an evaluation of extra-intestinal manifestations. Symptom based physical examinations will be performed at all other visits at a minimum, but evaluation of EIMs will still be completed at every study visit.

Subjects will undergo a full colonoscopy with biopsy for histologic assessment during Screening with local investigator assessment for Mayo endoscopic subscore for initial eligibility assessment, confirmed by a central reader prior to randomization. At end of treatment (Week 8 in Part 1) a full colonoscopy or flexible sigmoidoscopy, depending on the extent of disease at Screening, will be performed.

For subjects in Part 2, an endoscopy will be performed at Week 16/PD. A flexible rectosigmoidoscopy is recommended at Week 16/PD, however, the use of flexible rectosigmoidoscopy or colonoscopy will be based on the investigator's discretion per local practice.

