5.2.1 Inclusion Criteria

A subject will be eligible for study participation if he/she meets the following criteria:

1. Male or female ≥ 16 and ≤ 75 years of age at Baseline.
 - Adolescent subjects at the age of 16 and 17 years old will be enrolled if approved by the country or regulatory/health authority. If these approvals have not been granted, only subjects ≥ 18 years old will be enrolled
 - Adolescent subjects at the age of 16 and 17 years old must weigh ≥ 40 kg and meet the definition of Tanner Stage 5 (refer to Appendix H) at the screening Visit

2. Diagnosis of UC for 90 days or greater prior to Baseline, confirmed by colonoscopy during the Screening Period, with exclusion of current infection, colonic dysplasia and/or malignancy. Appropriate documentation of biopsy results consistent with the diagnosis of UC, in the assessment of the investigator, must be available.
3. Active UC with an Adapted Mayo Score of 5 to 9 points and endoscopy subscore of 2 to 3 (confirmed by central reader).
4. Demonstrated an inadequate response to, loss of response to, or intolerance to at least one of the following treatments including, oral aminosalicylates, corticosteroids, immunosuppressants, and/or biologic therapies, in the opinion of the investigator, as defined below:

Note: An inadequate response, loss of response, or intolerance to Oral Aminosalicylates will NOT count towards eligibility for the following countries: Austria, Czechia, Finland, France, Ireland, Italy, Latvia, Lithuania, Norway, Poland, Portugal, Spain, Sweden and United Kingdom.

- Oral aminosalicylates (e.g., mesalamine, sulfasalazine, olsalazine, balsalazide)
 - Signs and symptoms of persistently active disease, in the opinion of the investigator, during a current or prior course of at least 4 weeks of treatment with 2.4 g/day mesalamine, 4 g/day sulfasalazine, 1 g/day olsalazine, or 6.75 g/day balsalazide.
- Corticosteroids
 - Signs and symptoms of persistently active disease despite a history of at least one induction regimen that included a dose equivalent to prednisone ≥ 40 mg/day orally for at least 3 weeks or intravenously for 1 week, OR
 - Unable to taper corticosteroids to below a dose equivalent to prednisone 10 mg daily orally without recurrent active disease, OR
 - Signs and symptoms of persistently active disease during or after a course of at least 4 weeks of treatment with 9 mg/day budesonide or 5 mg/day beclomethasone, OR

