#### 8.1 General Considerations

The efficacy analyses for the 8-week DB induction period (Part 1) will be conducted in the ITT1 population. The efficacy analyses for the 8-week OL extended treatment period (Part 2) will be conducted in the ITT2 population. All tests will be at the  $\alpha$  level of 0.05 (2-sided). "Baseline" refers to the last non-missing observation prior to the first administration of the study drug or prior to the randomization if no study drug is given.

Unless otherwise specified, categorical variables will be analyzed using Cochran-Mantel-Haenszel (CMH) test, stratified by bio-IR status (bio-IR vs. non-bio-IR), Baseline corticosteroid use (yes vs. no) and Baseline Adapted Mayo score (≤ 7 vs. > 7). Any subject who was randomized under the wrong stratum will be analyzed according to the actual stratum the subject belongs to. Continuous variables collected longitudinally will be analyzed using Mixed-Effect Model Repeat Measurement (MMRM) method. Continuous variables collected at only one post-baseline visit (such as Mayo score) will be analyzed using an Analysis of Covariance (ANCOVA) model.

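### Ranked endpoints 6 and 7 can already be met at Baseline, and the planned CMH test does not use Baseline symptom status, which costs precision though not validity

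*SAP*

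**What the plan says.** SAP Section 3.2 lists "The achievement of no bowel urgency at Week 8" as rank 6 and "The achievement of no abdominal pain at Week 8" as rank 7. Both are absolute states with no Baseline condition. The Protocol synopsis gives the measurement: "Proportion of subjects who report no abdominal pain and proportion of subjects who report no bowel urgency in the 3 days will be estimated". SAP Section 4.0 uses all of ITT1 for Part 1 efficacy.

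The disease-activity entry criterion in Protocol Section 5.2.1 is "Active UC with an Adapted Mayo Score of 5 to 9 points and endoscopy subscore of 2 to 3". By SAP Section 3.0 the Adapted Mayo score is the full score without the physician's global assessment, which leaves stool frequency, rectal bleeding and endoscopy. No inclusion criterion asks for urgency or pain.

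SAP Section 8.1 stratifies the CMH test by bio-IR status, Baseline corticosteroid use and Baseline Adapted Mayo score. Baseline urgency and pain are not among these strata, the subgroups in SAP Section 8.7 or the Baseline characteristics in SAP Section 7.1. The Baseline value enters only the imputation model of SAP Section 8.3.1. Under NRI-C that model decides the result only for data missing because of COVID-19.

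The data exist. The eDiary is dispensed at Screening (Protocol Section 5.3.1.1, Subject Diary) and records both symptoms (Protocol Section 10.3).

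**The concern.** Of the twelve endpoints in the fixed sequence, only these two can be satisfied at Baseline. The primary endpoint and ranks 1, 2, 5 and 10 need an endoscopic subscore of 0 or 1, which entry at 2 to 3 rules out. Ranks 3, 4, 8, 9 and 11 are changes from Baseline. For the two continuous endpoints the SAP adjusts for the Baseline value (Section 8.3.2); for ranks 6 and 7 the CMH test does nothing comparable.

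A subject who reports no urgency or pain in the Baseline window and none at Week 8 counts as an achiever, in either arm, without having improved. Two things follow. The reported rates blend resolution with prior absence, and as planned the report need not show how large that second part is. A variable likely to predict the outcome strongly also stays in the error term, so the interval is wider than it has to be. Because testing follows a fixed sequence (SAP Section 12.0), a miss at rank 6 or 7 would end formal testing of the ranks below it.

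**Working it through.** **The plan's own figure.** SAP Section 2.4 says that "a sample size of 154 subjects in placebo and 308 subjects in upadacitinib dose will have > 95% power", using "two-sided Fisher's exact test at a 0.05 significant level", where "clinical remission rate is assumed to be 5% in the placebo group and 18% in the upadacitinib 45 mg QD treatment group". Exact enumeration of Fisher's test gives 98.9%, so the statement reproduces. It concerns the primary endpoint only; no rates or power are given for ranks 6 and 7.

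**Inputs for ranks 6 and 7.** From the documents: 308 and 154 subjects, two-sided 0.05. Assumed, because the documents are silent: the symptom-free share at Baseline, *f*, and the Week 8 rates.
- Scenario A (larger effect), placebo vs upadacitinib: 20% vs 45% among symptomatic subjects, 80% vs 90% among symptom-free subjects.
- Scenario B (smaller effect): 15% vs 30% among symptomatic subjects, 70% vs 80% among symptom-free subjects.

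The three planned strata and missing data are not modelled.

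**Formulas.** Let *p* and *u* be the placebo and upadacitinib rates within a Baseline group.
- Overall rates: P = f·p(free) + (1−f)·p(sympt), and U likewise; d = U − P.
- Variance without the stratum: V0 = U(1−U)/308 + P(1−P)/154.
- Variance with it (weights proportional to stratum size): V1 = Σ w·[u(1−u)/308 + p(1−p)/154], with w = f and 1−f.
- Power = Φ(d/√V − 1.96).

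**Worked case, Scenario B, f = 30%.**
- P = 0.3×0.70 + 0.7×0.15 = 0.315; U = 0.3×0.80 + 0.7×0.30 = 0.450; d = 0.135.
- V0 = 0.2475/308 + 0.2158/154 = 0.002205, SE 0.0470. Power = Φ(2.875 − 1.96) = 82.0%.
- V1 = 0.3×(0.16/308 + 0.21/154) + 0.7×(0.21/308 + 0.1275/154) = 0.001622, SE 0.0403. Power = Φ(3.352 − 1.96) = 91.8%.
- Variance cut = 1 − 0.001622/0.002205 = 26%.
- Share of placebo achievers already symptom-free at Baseline = 0.21/0.315 = 67%.

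**Across the range.**

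| Scenario | f | d (points) | Variance cut | Power without → with stratum | Placebo achievers symptom-free at Baseline |
|---|---|---|---|---|---|
| A | 2% | 24.7 | 3% | above 99.9% both | 8% |
| A | 5% | 24.3 | 7% | above 99.9% both | 17% |
| A | 10% | 23.5 | 13% | above 99.9% both | 31% |
| A | 20% | 22.0 | 22% | 99.7% → 99.9% | 50% |
| A | 40% | 19.0 | 31% | 97.5% → 99.7% | 73% |
| B | 2% | 14.9 | 3% | 96.4% → 96.9% | 9% |
| B | 5% | 14.8 | 8% | 95.2% → 96.5% | 20% |
| B | 10% | 14.5 | 14% | 92.8% → 95.8% | 34% |
| B | 30% | 13.5 | 26% | 82.0% → 91.8% | 67% |

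The difference d is the same with and without the stratum; only its variance changes. A wider grid of assumed rates with f from 5% to 30% gave variance cuts of 2% to 36%.

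**Validity.** In 200,000 simulated trials, type I error of the unadjusted test was 5.02% at f = 10% and 5.08% at f = 30%.

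**Restriction instead of stratification.** Limiting the test to subjects symptomatic at Baseline gives 89.8% power in Scenario B at f = 30%, below the stratified 91.8%. With 30% vs 45% among symptomatic subjects, 70% vs 80% among symptom-free subjects and f = 30%, restriction gives 76.9%, against 79.0% without the stratum and 84.1% with it.

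**The case against.** The planned test is sound. Randomisation balances symptom-free subjects on average, and the CMH strata follow Protocol Section 8.1.6.2. Protocol Section 4.0 states the objective as achieving no urgency and no pain, which is a state at Week 8, and neither document promises resolution among symptomatic subjects. Other endpoints also contain absolute states: a rectal bleeding subscore of 0 is part of the primary endpoint and can be present at entry (stool frequency 3 plus endoscopy 2 makes 5). The proposed factor was not a randomisation factor. In Scenario A power is already at least 97.5%, so the gain is at most about 2 points. The symptom-free share is unknown, and Protocol Section 3.0 names rectal urgency among the hallmark symptoms, so for rank 6 it may be very low. The planned strata may also recover some of the loss.

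Nearly all of this stands, and it limits the point to efficiency and interpretation. The rectal bleeding example does not carry over, because the endoscopic component still prevents the primary endpoint as a whole from being met at Baseline. An unknown share argues for reporting it, since adding the stratum costs little if the share proves small.

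A reader might infer more than the documents support:
- That the comparison is biased. It is not; see the type I error above.
- That these achievers never had the symptom. A 3-day diary window shows only that they did not report it then.
- That Baseline status is ignored altogether. It is in the imputation model.
- That stratifying removes the dilution. It leaves the difference unchanged.
- That ranks 8 to 11 are in real danger. That depends on a smaller effect together with a sizeable symptom-free share, and the documents establish neither.

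**Conclusion.** The point holds as one of precision and interpretation. The planned test of ranks 6 and 7 is valid and answers the stated objective, but it leaves out a Baseline variable that is already collected, and its achiever rates cannot be read as resolution rates. Stratifying cuts the variance by about 3% to 8% if 2% to 5% of subjects are symptom-free at Baseline and by 13% to 31% if 10% to 40% are. The power gain is negligible to about 2 points for 20% vs 45% among symptomatic subjects. For 15% vs 30% it is 3 points at 10% symptom-free and about 10 points at 30%. All these figures rest on assumed rates and ignore the planned strata. The case is stronger for pain than for urgency. The change is worth making because it is cheap.

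**What to change.** Before unblinding:
- For ranked endpoints 6 and 7 only, add Baseline status of the symptom concerned (present vs absent in the Baseline 3-day diary window, by the same rule as at Week 8) as a CMH stratification factor. State it in SAP Sections 8.1 and 8.5.1 and in the per-imputation CMH of Section 8.3.1, and record it in Section 13.0 as a change from the protocol.
- Keep the ITT1 population and the endpoint definitions.
- Add Baseline frequency of each symptom by arm to the tables of SAP Section 7.1.
- Add a supportive analysis of each endpoint in subjects with the symptom at Baseline, and rest any statement about resolution on it. Keep it supportive, because restriction can lower power.

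The cost is SAP wording and one derived variable per endpoint. The downside is up to 16 strata instead of 8, about 29 subjects each on average (462/16), with some sparse. At 10% symptom-free, about 15 placebo subjects would spread over 8 cells, roughly 2 each, and a stratum with only one arm contributes nothing to the test. If unblinding has already happened, the Baseline table and the supportive analysis remain worthwhile, labelled post hoc.
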